Prior to statistical analysis, all outcome and covariate data will be summarized with descriptive statistics, outliers examined, distributions identified and normalizing transformations applied where indicated. All of the above analyses will be based upon the intention-to-treat principle. The missing data mechanism (MCAR, MAR) for all outcomes and covariates will be assessed and, in the event of a non-ignorable mechanism, analyses will subjected to the methods of Diggle and Kenward³⁹ for continuous measures or Ibrahim and Lipsitz⁴⁰ for safety outcomes. Bone turnover markers will be log-transformed prior to analysis. Inferential testing will use a 5% two-tailed type I error rate with no adjustment for multiplicity taken for primary outcome analyses. Secondary efficacy analyses type I error rates will be adjusted by Bonferroni method whereas secondary safety analyses will not. In keeping with the objective of proposed exploratory analyses to generate data patterns consistent or inconsistent with improved bone quality, no adjustment for multiplicity will be taken. No interim efficacy analyses are planned. The statistical analysis plan will be modified to account for the adaptive randomization procedure, which is relevant to Aim 1 only.

AIM 1:

Primary efficacy outcome analysis: Analysis of covariance (ANCOVA) comparison of between-group (treated vs placebo) differences in mean change in LS aBMD (g/cm^2) by DXA from pre-treated baseline to 6 months of assigned treatment with adjustment for the following continuous baseline variables LS aBMD (g/cm^2), age (years) and weight (kg).

Primary safety outcome analysis: Fisher's Exact test of between-group difference in the number of people in each assigned group reporting at least one hypercalcemia or hypercalciuria event in the first 6 months of assigned treatment; followed by Cox proportional hazards model analysis of the between-group difference in the time-to-first hypercalcemia or hypercalciuria event; followed by GEE testing of the between-group difference in the temporal pattern of the repeatedly sampled hypercalcemia or hypercalciuria events in the first 6 months of assigned treatment.

Secondary efficacy outcome analyses: TH, FN and 1/3 Radius aBMD by DXA will analyzed by ANCOVA as described for the primary outcome, above.

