Primary efficacy outcome: For the primary endpoint of between-group difference in LS BMD at 6 months, power calculation assuming the proposed two-group ANCOVA and outcome correlation with baseline covariates of 0.3, we will have >90% power to detect a difference of $3.7 \pm 3.3\%$ in the TPTD-treated vs. $0.8 \pm 2.9\%$ in the placebo-treated group (placebo estimate based on interpolation from our preliminary data at 12 months). The estimated effect size is consistent with an annual TPTD-induced increases of 7.0-13.5% in studies by Arlot et al. in postmenopausal women, Langdahl et al. in premenopausal women with GIOP, and Kurland et al. in male IOP³⁶.

Primary safety outcome: For our primary safety outcome, the between-group difference in the number of people in each assigned group reporting at least one hypercalcemia or hypercalciuria event, we do not expect to have sufficient power to detect group differences in event rate because of the rarity of TPTD-related safety events observed in our pilot study and reported by others in the literature. Secondary efficacy outcome: For our secondary efficacy endpoints of between-group differences in TH, FN and 1/3R, our preliminary data suggest that we will not have sufficient power to detect between groups differences in these measures at 6 months, as the increases are less pronounced than at the LS. Secondary safety outcome: While we will closely examine the safety data, our small sample size provides minimal power to detect any but the most dramatic differences in safety profile between groups.

AIM 2:

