negative pregnancy test, all will have BMD, VFA and body composition by DXA. Women who fulfill BMD or fracture eligibility criteria will complete a Historical Questionnaire (Appendix 1) on medical and reproductive history (menstrual history, menarchal age, parity, OCP use), risk factors for osteoporosis (eating disorders, alcohol, tobacco, caffeine intake), personal and family history of fractures, current and past medications. The Eating Disorder Examination - Questionnaire (EDE-Q; Appendix 2) will be given to identify women with subclinical eating disorders^{45,46}. All will have a standardized physical (weight, height by Harpenden stadiometer) by a physician co-investigator and a Secondary Osteoporosis Evaluations (SOPEval). The following must be normal: blood count, Westergren ESR, C-reactive protein, electrolytes, creatinine, thyroid and liver function tests, uric acid, calcium, phosphate, 25-OHD (>20 ng/dl; those with levels between 21-29 ng/ml will be offered supplementation to achieve levels >30), intact PTH (<65 pg/ml), tissue transglutaminase IgA antibody (tTG; 99% specific and 95% sensitive for celiac disease) and immunoglobulin A (IgA) to exclude celiac disease, 24-h urine for creatinine, calcium (<300mg/gCr) (100-250 mg), free cortisol. Other tests may be performed if less common etiologies are suspected. In some cases, arrangements may be made for some portions of the screening visit procedures (eg laboratory studies) to take place outside of this medical center. In all cases, eligibility will be verified by study physicians.

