Subjects will be provided with calcium (citrate) caplets (Citracal + D; each 315 mg + 250 IU D) and a multivitamin (Centrum) that provides 500 IU of vitamin D daily. Most subjects will be instructed to take 2 Citracal caplets and a multivitamin; the total daily dose of calcium from supplements will be approximately 630 mg and of vitamin D 1000 IU. Subjects with very low dietary calcium intake (<500 mg/d estimated by interview and the FFQ), will be asked to take 3 Citracal caplets, while those with high dietary calcium intakes (>1,000 mg/day) will be asked to take 1 Citracal caplet.

Visits 4-5, 8-13 (Study Evaluations): At each study visit, study coordinators will assess any adverse events that transpired since the last study visit. Patients will be instructed to bring their Forteo journal and pens with them to every visit, which documents their compliance with the study medication. The purpose

of the 1-week and 1-month visits (Visits 4 & 5) is to monitor for compliance and adverse effects. At the 1-week and 1-month visit, we will also obtain fasting serum for serum calcium (safety) and at the 1-Month we will also collect serum for BTMs. These visits may be conducted on site for women who reside close to the study sites or may be a telephone contact and local blood draw for those who live at a distance. The remainder of the study visits to perform imaging studies and/or blood draws and dispense study drug are shown in Tables 1-3. We will perform a single follow-up cQCT scan after 24 months of TPTD treatment to minimize radiation exposure in these women who are of child-bearing age. At Visit 12, subjects will be presented with three options for post-TPTD follow up as described in the study design.

Visit 6 (Pre-Biopsy Clearance and Labeling): Subjects will have a pre-biopsy clearance visit with the surgeon and have safety bloods drawn and processed as per hospital regulations. Subjects will receive their second antibiotic labeling agent, demeclocycline, and accompanying labeling schedule.

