c. Hypercalcemia, Hyperuricemia and Hypercalciuria: Hypercalcemia and mild increases in serum uric acid are known side effects of PTH, although not very common at the FDA-approved 20 mcg/day dose that we will use. A post-hoc analysis of two prospective randomized clinical trials involving 1,637 postmenopausal women and 2,437 men found that urinary calcium excretion increases by an average of 32 mg/d on the 20 mcg dose of TPTD⁶⁷. [name], the Study Monitor, will monitor pre-dose serum calcium and uric acid and urinary calcium excretion at 1 to 6-month intervals to determine the incidence of these abnormalities in our study participants. We will exclude subjects with hypercalcemia (fasting serum calcium >10.2 mg/dl) and hypercalciuria (>300 mg/g creatinine) at baseline.

For subjects in the placebo group during months 0-6, there may be a risk of bone loss. However, Peris et al. reported a retrospective analysis of 16 women with IOP, managed with calcium, vitamin D and increased physical activity⁶⁸ They documented small increases in BMD and no fractures over an average 3 years of observation, supporting the safety of a placebo-controlled design. We have longitudinal BMD data in 18 women with IOP followed on calcium (1000-1500 mg/day) and vitamin D (800-1000 IU/day) for an average of 4 years. LS BMD increased by $0.8 \pm 2.9\%$, while there were slight decreases at the FN (-1.2 ± 5.3%), TH (-0.5 ± 3.4%) and 1/3 Radius (-2.4 ± 2.8%). None of the decreases were statistically significant. Thus, we do not expect major declines in BMD in the women randomized to placebo for the first 6 months and in any case, all subjects will receive teriparatide after the first 6 months.

2) Radiation

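### The Aim 1 primary safety analysis compares calcium between arms only as a yes/no event, with low power the plan concedes; a baseline-adjusted comparison of the measured values should be added beside it

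*Combined protocol and SAP*

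**What the plan says.** Section 2.A, Aim 1, defines the primary safety outcome as the "number of people in each assigned group reporting at least one hypercalcemia or hypercalciuria event in the first 6 months of assigned treatment". It is tested by Fisher's exact test, then by a Cox model for time to first event, "followed by GEE testing of the between-group difference in the temporal pattern of the repeatedly sampled hypercalcemia or hypercalciuria events". All three use the same binary event. The section gives no threshold, unit or sampling time for it. On error control it says: "Inferential testing will use a 5% two-tailed type I error rate with no adjustment for multiplicity taken for primary outcome analyses".

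The numerical limits are elsewhere and concern entry. Section 11, item 1c: "We will exclude subjects with hypercalcemia (fasting serum calcium >10.2 mg/dl) and hypercalciuria (>300 mg/g creatinine) at baseline". Section 3.A, Visit 1, lists "24-h urine for creatinine, calcium (<300mg/gCr) (100-250 mg), free cortisol" among the tests that must be normal, which places a second urine range beside the first.

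Section 11 also reports, from earlier trials, that "urinary calcium excretion increases by an average of 32 mg/d on the 20 mcg dose of TPTD". Section 2.B says of the safety comparison: "we do not expect to have sufficient power to detect group differences in event rate because of the rarity of TPTD-related safety events".

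Table 1, whose layout is partly broken, appears to place 24-h urine calcium/creatinine at screening, 1 month and 6 months. Section 3.A schedules fasting serum calcium at 1 week and 1 month. Section 2 gives every woman teriparatide from month 6.

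**The concern.** Urine and serum calcium are the laboratory values on which the plan expects teriparatide to act, and it cites a size for the urinary effect. Yet sections 2.A and 2.B contain no between-arm comparison of those values as measured. They enter inference only as crossed or not crossed, against a line that the analysis section does not state. With 28 and 13 women, such a count carries little information about a modest average rise. After month 6 there is no untreated arm, so whatever the randomised phase can show about calcium must come from these six months. If only the event analyses are run, the likely report is a non-significant count that neither supports nor excludes the cited rise, while values that could give an estimate with an interval go unused.

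**Working it through.** **Inputs from the documents.** Allocation 28:13 (section 2); two-sided 5%, no adjustment for primary outcomes (2.A); cited urinary rise 32 mg/d (section 11); limits >10.2 mg/dl and >300 mg/g creatinine, stated for entry only (section 11). No calcium mean, SD or placebo event rate is given. Section 2.B's statement on power is qualitative, so there is no figure to reproduce.

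**Step 1. What Fisher's test needs at 28 v 13 (no variability assumption).**

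| Placebo events | Teriparatide events | Two-sided p |
|---|---|---|
| 0/13 | 7/28 | 0.077 |
| 0/13 | 8/28 | 0.040 |
| 1/13 | 11/28 | 0.064 |
| 1/13 | 12/28 | 0.033 |

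Exact power is the sum of Bin(a; 28, p₁) × Bin(b; 13, p₀) over all tables with p ≤ 0.05. For placebo 10% v teriparatide 20% it is 4.9%; for 10% v 30%, 20.4%. For about 80% power the teriparatide rate must reach roughly 35%, 47% or 54% when the placebo rate is 0%, 5% or 10%.

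**Step 2. Fisher power for a rise near 32 mg/d (assumed distributions).** This step applies the entry limits on treatment, which is an inference, and treats 32 mg/d as about 30–32 mg/g creatinine, that is, roughly 1 g creatinine per day.

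- Grid A: urine mean 130–200 mg/g, between-woman SD 40–60, within-woman CV 15–35%; serum mean 9.3–9.5 mg/dl, between-woman SD 0.25–0.30, within-woman SD 0.15–0.25; 2 urine and 3 serum readings. Fisher power runs from about 0% to 13%. The top case has event rates of 17.8% v 34.0%, power 12.7%.
- Grid B: log-normal urine, median 120–180 mg/g, between-woman log-SD 0.35, within-woman log-SD 0.2–0.4; serum 9.4 mg/dl, SDs 0.25 and 0.20; 2 urine and 4 serum readings; +30 mg/g on teriparatide. Over nine scenarios Fisher power is 0.2–7.5%. In the central case (150 mg/g, log-SD 0.3) the rates are 10.0% v 17.4% and power is just under 3%.

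With no drug effect, the share of women with an event is about 0.3–25% on grid A and 3–24% on grid B. That width shows how little the documents fix this figure.

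**Step 3. The same shift analysed as a measured value.**

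- Mean change in mg/d: noncentrality = 32 / (SD × √(1/28 + 1/13)) = 32 / (0.3356 × SD), 39 df. With SD 50 this is 32 / 16.78 = 1.91.

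| Assumed SD of change (mg/d) | 30 | 40 | 50 | 60 | 80 | 100 |
|---|---|---|---|---|---|---|
| Power | 87% | 64% | 46% | 34% | 21% | 15% |
| 95% CI half-width (mg/d) | 20 | 27 | 34 | 41 | 54 | 68 |

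The half-width is 2.023 × 0.3356 × SD.

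- ANCOVA of mean log urine calcium/creatinine (months 1 and 6) on its log screening value, grid B, 3,000 simulated trials per scenario: power 27–88%, central 48%.

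Together, the urine comparison has roughly 15–90% power, against 0–13% for the count. In every grid B scenario the ANCOVA had the higher power on the same simulated women.

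**The case against.** **The low power is disclosed and the study is called exploratory.** True: section 2.B says so and section 1 describes the study as exploratory. The count's weakness is therefore not a hidden error. Disclosure does not explain why the measured values go unanalysed.

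**A count of women over a limit is a legitimate safety summary, and the mean rise is already known from other trials.** This also stands. A mean difference answers a different question, so it can sit beside the count but not replace it.

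**Power for the continuous comparison is not assured.** Correct: with an SD of change of 60 mg/d or more it is about one third or less. The case rests on reporting an estimate and interval, not on reaching significance.

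**Stronger readings.** A reader might infer that the entry cut-offs are the event definition, that a single reading just over the line counts, and that about 10% of women would become events through noise. The documents do not support this. No passage applies the cut-offs on treatment, and the 10% depends on variability figures they do not contain. The plan's remark that such events were rare in the pilot also sits awkwardly with it: the modelled 17.4% would mean about 3.7 of 21 pilot women (0.174 × 21), although the pilot's event definition is not given. A reader might also blame the supplements supplied from Visit 3 ("Subjects will be provided with calcium (citrate) caplets"). Both arms receive them, so randomisation covers the comparison, and no size of effect is given.

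**Conclusion.** The concern holds in a limited form. Calcium is compared between arms only as a binary event with no stated on-treatment threshold, and the measured values from the only randomised period are not compared. The requirement of 8/28 against 0/13 follows from the allocation alone. The 0–13% for Fisher's test and roughly 15–90% for the continuous urine comparison rest on assumed calcium distributions, on reading the entry limits as event limits, on equating mg/d with mg/g creatinine, and on 24-h urine being collected at 1 and 6 months as Table 1 appears to show. The direction is consistent across the assumptions tried; the size of the gain is not established. No figure can be given for serum calcium, because the documents cite no serum rise. The missing threshold alone is an omission of detail. This is a cheap improvement to the analysis, not a flaw that invalidates the planned tests.

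**What to change.** In section 2.A, Aim 1, primary safety:

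1. Keep the Fisher, Cox and GEE analyses of the unfiltered event.
2. Add a pre-specified ANCOVA of log 24-h urine calcium/creatinine (mean of the 1- and 6-month collections) on its log screening value, and the same for pre-dose serum calcium on its baseline. Report each as a between-arm difference with a 95% CI; the log urine difference back-transforms to a ratio. Present them as supporting estimates.
3. State which threshold, units and sampling times define an event for analysis, and reconcile the two urine ranges in section 3.A with the exclusion limit in section 11. Which limit is right is for the investigators.
4. Do not require a minimum rise from baseline before counting an event. In the central grid B case, requiring a rise beyond 1.96 × √2 × the within-woman SD cuts the rates from 17.4% v 10.0% to about 4.8% v 2.1%. That removes about 72% of the teriparatide-arm events (1 − 4.8/17.4) and takes Fisher power below 0.1%.

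Cost: SAP wording and one or two extra analyses on values that appear to be collected already. No new visits or samples are needed, and clinical management is unchanged. Section 2.A already says the plan will be modified for Aim 1, so the text can go into that revision. The limitation to record is that a mean difference does not show how many women exceed a limit, so both results must be reported.

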The major objective of this protocol is a therapeutic one, namely to establish the safety and efficacy of TPTD in premenopausal women with IOP in a phase 2 clinical trial. We hypothesize that osteo-anabolic therapy with TPTD will improve areal and vBMD in premenopausal women with IOP. We also hypothesize that TPTD will restore abnormal microarchitecture toward normal and improve other aspects of bone quality in premenopausal women with IOP. The primary aim of this research study will be to establish the efficacy and safety of 6 months of TPTD versus placebo in premenopausal women with IOP. Secondary aims are to determine the extent to which 12 and 24 months of TPTD improves areal and volumetric BMD, bone microarchitecture and stiffness compared to baseline measures in premenopausal women with IOP and to determine whether baseline bone turnover, as assessed by quadruple tetracycline labeling predicts response to TPTD. This study will have high impact on clinical practice as it pertains to the management of premenopausal women with IOP. This study is exploratory and will not support any new labeling claims for Forteo in the premenopausal patient population.

For the sub-study: We aim to investigate the pharmacokinetics (pK) and pharmacodynamics (pD) of teriparatide (Forteo) to determine if subject weight influences pK or pD. To develop preliminary data necessary to plan larger studies on this issue, we aim to study 6 subjects already enrolled in this study (AAAF2251) who are already in the open label treatment period. We will enroll 3 normal weight subjects (BMI between 18.5 kg/m2 and 24.9 Kg/m2) and 3 overweight or obese subjects (BMI equal to or greater than 25 kg/m2). All subjects will be offered participation until enrollment goals for the sub-study will be met.

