randomized, double blind, placebo-controlled, single switch-over trial of TPTD in premenopausal women with IOP. Forty-one subjects will be assigned to TPTD (Group A; n=28) or placebo (Group B; n=13). At the 6 month timepoint, all subjects will receive TPTD, but blinding of original group assignment will be maintained for an additional 6 months. At the 12 month visit, the blind will be broken and those initially randomized to TPTD (Group A) will continue on study drug for an additional 12 months while those initially randomized to placebo (Group B) will continue for an additional 18 months, so that subjects in both groups complete 24 months of treatment overall. aBMD by DXA and HRpQCT will be measured at baseline and at 6 month intervals. vBMD by cQCT will be performed before randomization and after 24 months of TPTD (Table 1). A quadruple labeled transiliac crest bone biopsy will be performed at 3 months for both Group A and B. Eli Lilly & Company will provide TPTD and placebo but will supply no other funding. After 24 months of treatment in either Group A or B, all women will be offered three choices for follow up: the subjects can A) continue to to be followed for 12 months off TPTD B) choice to leave the study and be treated clinically using an anti-resorptive medication to maintain gains in bone density after treatment with TPTD, or C) join a new study to maintain gains in bone density after treatment. The new study is currently in the design phase and funding phase and precise details are not yet available.

Statistical Analysis Plan

2.A. Statistical Analysis Plan Our aims in this protocol are as follows:

Aim 1: To establish the efficacy and safety of 6 months of TPTD versus placebo in premenopausal women with IOP

Aim 2: To determine the effect of 3 months of TPTD on bone remodeling at the tissue level and the extent to which baseline and 3 month bone remodeling predicts response to TPTD in premenopausal women with IOP.

Aim 3: To determine the extent to which 12 and 24 months of TPTD improves areal and volumetric BMD, bone microarchitecture and strength (stiffness) compared to baseline measures in premenopausal women with IOP

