Secondary safety outcome analyses: Fisher's Exact test will be used to assess treatment group differences in numbers of people endorsing each symptom reported on the symptom checklist administered at each study visit without adjustment for multiplicity. The GEE test approach proposed for the primary safety

outcome analysis of longitudinal events will be repeated for any symptom reported by >10% of either treatment group.

AIM 2:

Primary analysis: The between-group mean difference in the quad-labeled histomorphometric measured change in Mineralizing Surface (MdPm) and Bone Formation Rate (BFR/BS) at 3 months will be analyzed with ANCOVA with adjustment for the baseline continuous variables of age (years) and weight (kg.). Outcomes will be analyzed separately without adjustment for multiplicity. Secondary analyses: In the teriparatide-treated group the relationship between baseline MdPm and BFR/BS, and change in MdPm and BFR/BS in the first three months of treatment, and 12 and 24 month change in aBMD of the spine and hip by DXA and vBMD of the spine by cQCT will be assessed with multiple regression analysis. Per annum change in DXA and cQCT outcomes will be separately modeled as a function of baseline MdPm and BFR/BS, baseline level of the DXA or cQCT outcome, age, weight, bone microstructure by microCT of biopsy specimens, and change from baseline in MdPm and BFR/BS during the first three months. Other potential baseline predictors of DXA and cQCT response to teriparatide treatment will be explored with multiple regression to determine whether any clinical or constitutional measures supercede change in MdPm or BFR/BS in predicting bone change.

AIM 3:

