Visit 2 (Imaging): If the SOPEval is normal, candidates will be invited to proceed with Visit 2. Prior to initiation of any additional study procedures, an informed consent discussion will take place. Only after the informed consent (Study Consent Form) is signed will further research related procedures commence. The study will be described, including the bone biopsy procedure. Participants with fractures will be asked to bring verification (x-rays or radiology reports). They will complete standardized questionnaires to assess current diet and physical activity. We use the validated Block food frequency questionnaire (FFQ; Appendix 3)^{47,48} to assess calcium intake. Physical activity is assessed by the modified Baecke questionnaire (Appendix 4)⁴⁹⁻⁵¹. Equivocal VFA results will be evaluated with spine x-rays. Central QCT of the spine (L1 and L2) with additional single slice at L4, and HR-pQCT of the distal radius and tibia will be performed to measure volumetric BMD, body composition (subcutaneous and visceral adiposity), and cortical and Tb microstructure. Serum will be archived at -80°.At this visit, subjects will also receive tetracycline for their first round of antibiotic labeling and instructions with a scheduled dosing according to protocol. Subjects will complete labeling before the randomization visit, where they will receive Forteo and begin treatment.

52,53

Visit 3 (Randomization): During this visit, imaging results will be reviewed with the subjects. Eligible subjects who agree to participate will be randomized to TPTD or placebo (ratio 28:13) through block randomization with randomly varying block sizes of 2, 4 or 6, stratified by whether they are included on the basis of history of fractures or low BMD. Serum/urine will be archived at -80°C for batch analyses of specialized biochemistries. DNA will be obtained from peripheral blood lymphocytes for archival purposes. We will collect blood for the measurement of osteoblasts, or bone building stem cells, in the bloodstream.

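### As most naturally read, the Aim 2 prediction analysis is confined to Group A, and no baseline-only model is planned that would use the 13 Group B women

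*Combined protocol and SAP*

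**What the plan says.** Section 1 lists among the secondary aims to "determine whether baseline bone turnover, as assessed by quadruple tetracycline labeling predicts response to TPTD". It does not limit this to one arm. Aim 2 in section 2.A names both baseline and 3-month remodeling as predictors of response.

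The Aim 2 secondary analyses then set the population and predictors: "In the teriparatide-treated group the relationship between baseline MdPm and BFR/BS, and change in MdPm and BFR/BS in the first three months of treatment". The outcomes are 12- and 24-month DXA change and spine cQCT change. The regressors are baseline MdPm and BFR/BS, the baseline value of the outcome, age, weight, microCT structure from the biopsy, and "change from baseline in MdPm and BFR/BS during the first three months". No model with the baseline predictor alone is described.

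On the data available, section 2 states: "A quadruple labeled transiliac crest bone biopsy will be performed at 3 months for both Group A and B". Section 3.A (Visit 2) says of the first label set: "Subjects will complete labeling before the randomization visit". Section 2 extends Group B's dosing "so that subjects in both groups complete 24 months of treatment overall". Table 1 gives DXA at month 6, and Table 3 gives Group B DXA at months 18 and 30 and cQCT at month 30.

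**The concern.** The regression combines two questions with different data needs. Whether the early change on TPTD predicts response can be studied only in women who were on TPTD when the second labels were given, which means Group A. Whether baseline turnover predicts response needs only pre-treatment labels and a later course of TPTD, and both groups have these. Because the two predictors share one model, the restriction that the change predictor needs also falls on the baseline predictor.

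That leaves 13 of 41 women (32%) outside an analysis they could inform with data already scheduled. In a trial this small, a real association of moderate size is then easier to miss and its coefficient is estimated less precisely.

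**Working it through.** **Can Group B supply the baseline analysis?**

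| Item needed | Group A | Group B | Source |
|---|---|---|---|
| Labels before any TPTD | before randomization | before randomization | 3.A, Visit 2 |
| Biopsy to read them | month 3 | month 3 | section 2 |
| Last DXA before TPTD | baseline | month 6 | Table 1 |
| DXA after 12 and 24 months of TPTD | months 12, 24 | months 18, 30 | Tables 2, 3 |
| 3-month change on TPTD | yes | no; second labels are on placebo | 3.A, Visit 7 |
| cQCT interval | 24 months, all on TPTD | 30 months, 6 of them on placebo | section 2, Table 3 |
| microCT at biopsy | on TPTD | on placebo | section 2, 3.A |

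For DXA, Group B has everything the baseline question needs. It cannot supply the change predictor. Its cQCT interval and its microCT covariate do not match Group A's.

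**The plan's own figure.** Section 2.B states that 40% to 55% of variance is detectable, at 80% power and 5% alpha with up to 3 covariates, and words this for the 3-month change. I used the noncentral F test of one predictor with c covariates: df = 1 and n − c − 2, and λ = n·R²/(1 − R²). With c = 3 and n = 28 the detectable partial R² is 0.234. Reaching 0.415 to 0.553 would take n = 14 down to 10. The stated range therefore does not reproduce as one-predictor variance. Partial correlations for n = 22 to 41 (0.54 to 0.41) fall inside it, but the documents do not say that a correlation was meant. The present point does not rest on that figure, and no figure is given for the baseline predictor.

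**Effect of adding Group B.** Inputs are 28 and 13 women (section 2), two-sided 5% (2.A), and 10% drop-out (2.B), which gives 28 × 0.9 = 25.2 and 41 × 0.9 = 36.9. The covariates are pre-TPTD outcome value, age and weight (c = 3), plus original group when pooled (c = 4). A true R² of 0.20 is my assumption, so that R²/(1 − R²) = 0.25.

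| n | c | Error df | Detectable R², 80% power | λ at R² = 0.20 | Power at 0.20 |
|---|---|---|---|---|---|
| 28 (A) | 3 | 23 | 0.234 | 7.00 | 72% |
| 41 (A+B) | 4 | 35 | 0.168 | 10.25 | 88% |
| 25 (A) | 3 | 20 | 0.258 | 6.25 | 66% |
| 37 (A+B) | 4 | 31 | 0.184 | 9.25 | 84% |

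At an assumed R² of 0.15, power goes from 57% to 74% (n = 28 to 41). The coefficient's standard error scales by about √(28/41) = 0.83, a 17% reduction.

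**If Group B's slope is weaker.** Let Group B's slope be k times Group A's, with equal predictor and outcome variances and R² = 0.20 in Group A. The pooled R² is 0.20 × [(28 + 13k)/41]², and λ = 41·R²/(1 − R²).

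| k | Pooled R² | λ | Power, n = 41 |
|---|---|---|---|
| 1.00 | 0.200 | 10.25 | 88% |
| 0.75 | 0.170 | 8.37 | 80% |
| 0.50 | 0.142 | 6.76 | 72% |
| 0.25 | 0.116 | 5.39 | 62% |

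Group A alone gives 72%, so the gain is gone at about k = 0.5 and pooling costs power below that. The documents do not report how stable MdPm or BFR/BS is over six months.

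**Multiplicity.** Section 2.A applies Bonferroni to secondary efficacy analyses without giving a count. Assuming six tests (alpha 0.05/6), power at R² = 0.20 is 42% at n = 28 and 66% at n = 41.

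**The case against.** The restriction is inferred. The text names the teriparatide-treated group, not Group A, and from month 6 every woman is on TPTD. A reader might infer that the plan expressly excludes the 13 women; it does not say so. The broader reading does not solve the problem, however, because the model contains a 3-month on-treatment change that Group B lacks.

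The planned model is also coherent on its own terms. Change and microCT belong to Group A, and a baseline-only model in everyone changes the covariates as well as the sample. This is right, and it is why the new model should be an addition, with its omission of microCT stated.

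Group B's baseline labels are at least six months old when TPTD starts. An additive group term removes a difference in mean response and leaves a weakened slope uncorrected. This stands, and it makes the computed gain a ceiling. An interaction term can expose the problem only roughly: with equal predictor spread, its standard error is √(1/28 + 1/13)/√(1/28) = 1.78 times that of the Group A slope.

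The R² of 0.20 is not from the documents. At 0.40, the low end of the range in section 2.B, Group A alone already has 97% (n = 25) to 99% (n = 28) power and Group B adds almost nothing. That range is stated for the change predictor and does not reproduce, so this objection carries limited weight.

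**Conclusion.** The point holds as a modest, inexpensive improvement. On the natural reading, the baseline-turnover question is analyzed in Group A only, because it shares a model with a predictor that Group B cannot have, and no baseline-only model fills the gap. With equal slopes in the two groups, using all 41 women lowers the detectable partial R² by about 0.07 (0.234 − 0.168 = 0.066; 0.258 − 0.184 = 0.074 after drop-out) and adds 16 to 18 percentage points of power at an assumed R² of 0.20. These are upper bounds. They shrink if Group B's older labels predict less well, and absolute power is lower if the Bonferroni rule covers this analysis.

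Two stronger readings are not supported. A reader might infer that the planned analysis is biased; restricting it to Group A costs precision and introduces no bias. A reader might also infer that Group B's biopsies go unused; they are the comparator in Aim 2's primary between-group analysis. The primary endpoint is unaffected.

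**What to change.** Amend section 2.A, Aim 2 secondary analyses, as follows.

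- State that the existing model, with the 3-month change and microCT, is fitted in Group A, and keep it for the change predictor.
- Add a baseline-only DXA model in all 41 women. The outcome is change after 12 and 24 months on TPTD, measured from the last pre-TPTD scan (baseline in Group A, month 6 in Group B). The regressors are baseline MdPm or BFR/BS, the pre-TPTD outcome value, age, weight and original group.
- Omit microCT from this model and say why: the month-3 specimen is on TPTD in one group and on placebo in the other.
- Report Group A alone and the predictor-by-group interaction estimate with its confidence interval, as checks on equal slopes.
- As a sensitivity analysis, use Group B's second (on-placebo) labels, which lie closer to its TPTD start.
- Treat Group B's cQCT change as a sensitivity analysis only.
- Say whether these tests fall under the Bonferroni rule and how many there are.

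The cost is SAP text and a second, differently specified model to program and report. No visit, scan or biopsy is added.
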